The current proposal aims to conduct a multi-site randomized controlled trial comparing virtual-reality gaming delivery of CI therapy with (1) traditional clinic-based CI therapy of equal total duration and (2) a control group equating the dose of in-person therapy. Individuals with chronic stroke will be randomized to one of four different interventions: (1) traditional clinic-based CI therapy (35 therapist/client contact hours), (2) therapist-as-consultant virtual reality CI therapy (5 therapist/client contact hours in the clinic and 15 hours of independent game play at home), (3) therapist-as-consultant virtual reality CI therapy with additional therapist contact via telerehabilitation (5 therapist/client contact hours in the clinic, 6 brief contacts via teleconference, and 15 hours of independent game play in the home), and (4) 5 hours of standard occupational therapy. After 6-month follow-up, individuals assigned to standard OT/PT will cross over to a modified gaming therapy condition (a stand-alone application of the rehabilitation game without additional therapist contact). This crossover design is ethically responsible and will enable the team to test the feasibility and initial efficacy of a completely stand-alone implementation of the game, as well as to determine the effect of varying amounts of therapist contact on game-based rehabilitation outcomes (group 2 vs group 3 vs group 4 crossed over).

Table: Timeline of Participation

STUDY		THERAPY (weeks 2-4)			THERAPY	
ARM	Pre-tx	, , ,	Post-tx	6 month		
CI therapy	testing,	35 face-to-face hours, 15	testing,	follow-up		
	week 1	spent in active motor	week 5	testing		
		practice				
CI therapy		5 face-to-face hours, 15				
gaming (2)		hours in-home gaming				
CI therapy		5 face-to-face hours, 2.6				
gaming (3)		teleconsultation hours, 15				

	hours in-home gaming			
Standard	5 face-to-face hours		15 hours in-	Post-
care			home gaming	gaming
				testing

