Group 4, Traditional occupational/physical therapy focusing on the upper extremity. Five therapist/client contact hours will occur on approximate treatment days 1, 3, 6, and 11 (same schedule as gaming CI therapy). The treatment protocol was developed collaboratively by therapists on our Advisory Board given the question: "What protocol would you utilize if you were only given 5 contact hours to treat a client [with mild/ moderate hemiparesis]?" Although responses differed somewhat regarding the relative amounts of time devoted to the following activities, an average protocol was constructed consisting of the following: 1-hour progressive resistance exercise to establish and progress an upper extremity home exercise program, 2 hours of neuromuscular reeducation, and 2 hours functional practice on ADLs with verbal encouragement to use the more affected upper extremity to the largest extent possible. Home practice consists of stretching exercises, designed to increase range of motion, prescribed twice daily. After completing their participation in the standard OT condition (6 months), participants will be crossed over to a CI therapy gaming only condition. This condition will be identical to that described above, excluding therapist contact throughout the intervention. Following an initial consultation with a therapist, participants

will receive a DVD explaining the intervention and guiding them through self-management. The rationale for crossing over participants in the standard occupational therapy condition is two-fold: 1) this will allow testing the efficacy of a stand-alone implementation of the game (the only feasible treatment option for participants who are unable to access a clinic), and 2) it is ethically responsible given our hypothesis that the standard OT group will show inferior outcomes compared to the groups receiving CI therapy or gamified CI therapy.

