- A home program will be designed for all participants on the first visit. This home program will consist of theraband strengthening exercises to be done over a 15 minute time period twice daily (total of 30 minutes each day) except on the days that they come into the laboratory for treatment. Therapists will design this program based on the participant's skill with the exercises and the appropriate level of exertion (4 on the Borg CR10 Scale). Therapists will provide written instructions on these exercise and will review and modify the exercise program, as appropriate, on subsequent clinic visits (i.e., visits 2-4).

Allocation of treatment time – The first treatment session will be 2 hours in length and subsequent treatment sessions will each be 1 hour in length.

Treatment Day 1

Activity	Evaluate for	Neuromuscular	Functional	Progressive	Establish
category	therapeutic needs	re-education	Training	Strengthening	and teach
	_				home
					program
Time	25 minutes	20 minutes	25 minutes	25 minutes	25 minutes
dedicated					
to this					
activity					

Other Treatment Days

Activity category	Review and adjust, as appropriate, home program	Neuromuscular re- education	Functional Training	Progressive Strengthening
Time dedicated to this activity	10 minutes	10 minutes	25 minutes	15 minutes

Clinical Activity Description: Neuromuscular re-education (20 minutes TD1; 10 minutes TD2-4)

Description: ICD definition: (ICD 97112)Neuromuscular re-education of movement, balance, coordination, kinesthetic sense, posture, and/or proprioception for sitting and/or standing activities Examples include: Biofeedback, PNF, manual facilitation, sensory priming.

These activities will be used to "prime" the motor responses and promote more coordinated and appropriate muscle responses during the functional training to follow.

Clinical Activity Description: Functional Training (25 minutes all treatment days)

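### Only Group 2 v Group 3 is a randomised test of therapist contact; the crossed-over Group 4 leg should be labelled exploratory and non-randomised

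*Combined protocol and SAP*

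**What the plan says.** All references are to the combined protocol and SAP.

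- **Allocation.** Research Design and Detailed Study Procedures both state that "Individuals with chronic stroke will be randomized to one of four different interventions". The four are clinic CI therapy, gaming CI therapy (Group 2), gaming CI therapy with teleconsultation (Group 3) and standard therapy (Group 4). The stand-alone game is not among them.
- **Crossover.** Detailed Study Procedures: "After 6-month follow-up, individuals assigned to standard OT/PT will cross over to a modified gaming therapy condition". The Group 4 description repeats this: "After completing their participation in the standard OT condition (6 months), participants will be crossed over to a CI therapy gaming only condition".
- **Purpose.** Detailed Study Procedures give the crossover three uses: feasibility, initial efficacy of the stand-alone game, and "to determine the effect of varying amounts of therapist contact on game-based rehabilitation outcomes (group 2 vs group 3 vs group 4 crossed over"). The Group 4 description gives two reasons, one ethical and the other that "this will allow testing the efficacy of a stand-alone implementation of the game". It does not mention therapist contact as a question.
- **Therapist contact elsewhere.** Research Design assigns the question of added therapist monitoring to Group 2 v Group 3 and does not use the crossover for it.
- **Analysis.** The Data Analysis paragraph plans mixed models with treatment, time and their interaction as fixed effects and subject as a random effect, directed at the four treatment groups. It does not mention the crossover phase.

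**The concern.** The three-way comparison reads as a gradient of therapist contact: little in crossed-over Group 4, more in Group 2, most in Group 3. The plan says it will determine the effect of that gradient. But the lowest level is reached by a different route from the other two, so a difference between it and the others need not be due to therapist contact.

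The bias could run either way. If the earlier therapy had already produced part of the achievable gain, the stand-alone game would look too weak. If those still taking part at six months are the more motivated, it would look too strong. The protocol presents the stand-alone game as the realistic option for people who cannot reach a clinic, so a reader may take this comparison as evidence on how far therapist support can be withdrawn.

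**Working it through.** The plan states no figure for this comparison, so there is nothing to reproduce. The check is of the assignment, the timing and the analysis text.

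**1. Therapist contact by group**
- Group 2 (Self-Gaming checklist): 2 h + 3 × 1 h = 5 h.
- Group 3 (Tele-Gaming checklist): 5 h in clinic, plus 1 h + 5 × 20 min = 2.67 h by video, about 7.7 h in total. The timeline table gives the video part as 2.6 h.
- Crossed-over Group 4: Detailed Study Procedures describe the game without additional therapist contact. The Group 4 description has an initial consultation with a therapist, of unstated length, followed by a DVD. The lowest level of the gradient is therefore not clearly defined, and may not be zero.

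**2. What else differs when gaming starts**

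| Feature | Groups 2 and 3 | Crossed-over Group 4 |
|---|---|---|
| How the condition is reached | Randomised at entry | Whole arm, one direction, no second randomisation |
| Start of gaming | Weeks 2-4 | After the 6-month visit |
| Earlier study therapy | None | 5 h of standard therapy |
| Earlier home programme | None | 2 × 15 min = 30 min on non-clinic days |
| Earlier test sessions | One (pre) | Three (pre, post, 6 months) |
| Who can contribute | Those randomised | Those still taking part after 6 months |

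The 5 hours come from the Group 4 description: "Five therapist/client contact hours will occur on approximate treatment days 1, 3, 6, and 11 (same schedule as gaming CI therapy"). The home programme comes from the Usual Care materials: "theraband strengthening exercises to be done over a 15 minute time period twice daily". The Group 4 description instead speaks of stretching twice daily. Those two places need reconciling, but on either account Group 4 has had a home programme before gaming begins.

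**3. What randomisation supports**
- Group 2 v Group 3: concurrent, same game, differing by design in added teleconsultation. This is a valid randomised contrast of therapist contact.
- Crossed-over Group 4 v Group 2 or 3: membership of Group 4 was randomised, so whole sequences can be compared (standard therapy then stand-alone game v supported game from the start). That is not the effect of therapist contact.
- Within crossed-over Group 4: change from the 6-month visit to the post-gaming test, with no concurrent control.

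**4. Whether the analysis text compensates**

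It does not. There is no period or carry-over term, no stated baseline for the crossover phase, no handling of losses before crossover and no caveat.

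**5. Size**

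It cannot be derived. Two illustrations rest wholly on assumed inputs:
- *Selection.* If 20% of Group 4 never reach the game and would have gained 0.5 SD less than the rest, the mean gain of those who do is overstated by 0.20 × 0.5 = 0.10 SD. This is not the bias in the comparison, because Groups 2 and 3 may also lose participants.
- *False positives.* Suppose a two-sided 5% z-test were made with n per group, a true contact effect of zero and a net bias of b SD. With se = √(2/n), the rejection rate is 1 − Φ(1.96 − b/se) + Φ(−1.96 − b/se). For b = 0.2 and n = 20, se = 0.316, b/se = 0.632 and the rate is 9.7%. For n = 50, se = 0.2, b/se = 1 and the rate is 17.0%. For b = 0.3 the rates are 15.8% and 32.3%.

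**The case against.** The strongest reply is that little rests on this comparison. It is one clause of rationale. Aims 4a and 4b do not list it, the Group 4 rationale omits it, and Research Design already assigns the therapist-contact question to Group 2 v Group 3. Detailed Study Procedures claim only initial efficacy for the stand-alone game. Participants are at least six months post-stroke, the assessors are blinded, and Group 4's own post-treatment to 6-month interval offers a within-person lead-in.

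Most of this stands, and it limits the point. A reader might infer several stronger things that the documents do not support:
- *That the whole bracketed comparison is invalid.* It is not: Group 2 v Group 3 is randomised, and causal wording is acceptable there.
- *That a confounded significance test is planned.* The Data Analysis text specifies none for the crossed-over group, so the false-positive rates above describe a hypothetical test.
- *That Group 4 participants choose whether to cross over.* No opt-in is described. Attrition before six months is possible, but no rate is given.
- *That the crossover phase is uninformative.* It can give feasibility data and an uncontrolled estimate of change, with the lead-in interval as context.

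What remains is that the stated purpose includes crossed-over Group 4 in determining the effect of therapist contact, and nothing in the plan qualifies that leg.

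**Conclusion.** The concern holds for the crossed-over Group 4 leg only. That leg cannot separate therapist contact from prior treatment, period, test practice and attrition, and conclusions on therapist contact should rest on Group 2 v Group 3. Neither the direction nor the size of the net bias can be derived from the documents.

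It would be wrong to conclude that the trial's main result is compromised. The primary treatment-by-time models concern the four randomised groups and do not depend on the crossover. This is a correction to a supplementary inference. It is worth making because it changes what may be concluded about the stand-alone game. The verdict rests on the assignment and timing as written and needs none of the assumed figures.

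**What to change.** 1. In Detailed Study Procedures, keep the causal wording for Group 2 v Group 3 only, and state that conclusions on therapist contact rest on that contrast.
2. Report the crossover phase as within-group change from the 6-month visit with a 95% CI, with the numbers starting and completing and the hours played. Describe it as uncontrolled, both in Detailed Study Procedures and where the Group 4 description speaks of testing efficacy.
3. Label any comparison of crossed-over Group 4 with Groups 2 or 3 exploratory and non-randomised, and state the period, carry-over and attrition limits beside it. It need not be banned.
4. Reconcile Detailed Study Procedures with the Group 4 description on therapist contact after crossover, so that the condition being reported is defined.

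The cost is some rewording and a short addition to the Data Analysis text. No new data are needed. The downside is a weaker claim for the stand-alone game.

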Individuals with chronic stroke will be randomized to one of four different interventions: (1) traditional clinic-based CI therapy (35 therapist/client contact hours), (2) therapist-as-consultant virtual reality CI therapy (5 therapist/client contact hours in the clinic and 15 hours of independent game play at home), (3) therapist-as-consultant virtual reality CI therapy with additional therapist contact via telerehabilitation (5 therapist/client contact hours in the clinic, 6 additional brief teleconference sessions, and 15 hours of independent game play in the home), and (4) 5 hours of standard occupational therapy. The clinic-based CI therapy arm is the "gold standard" against which gaming therapy is compared (group 1 versus group 2 and group 3). The comparison to standard care (group 2 versus group 4) will demonstrate whether game-based treatment between therapy sessions enhances motor outcomes. The comparison between groups 2 and group 3 will determine the extent to which additional therapist monitoring via video conference improves treatment response of a home-based intervention. Motor function (Wolf Motor Function Test) and daily use of the more affected hand (accelerometry) will be measured prior to treatment, after treatment, and 6 months later.

Sample & Inclusion/Exclusion Criteria

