To promote the extended game-play required for CI therapy and enable customization to the user, the game utilizes procedural content generation (mathematical algorithms that generate game content based on therapist specifications and continuously change game scenery "on the fly"). The CI therapy principal of shaping (progressively increasing task difficulty as a person improves) is automated through the game. In just one example, bats flock around the avatar's head to encourage the user to raise the paretic hand above the shoulder and across the body. To disperse the bats, the player must "swat" the bats out of the way with the paretic hand. An introductory level of this gesture may require only that the paretic hand reaches above the level of the navel. As a person's range of motion improves, the game advances the player to reach across midline in addition to above shoulder level and, eventually, to higher above the shoulder and further across the body.

As with traditional CI therapy, the game also incorporates some elements of the "transfer package" that promote transfer of motor gains to daily activities. One such element is the Motor Activity Log (MAL). It is a highly structured self-monitoring interview that asks patients how effectively their more affected arm performed activities of daily living over the past 48 hours. Daily administration of the MAL is believed to be the most important element of the "transfer package" because it provides self-monitoring of arm use and problem-solving regarding how the client can incorporate use of the more affected upper extremity into his/her daily routine. To automate this self-assessment, the user matches his/her performance to a video of a stroke participant performing each task. If participants answers that he/she did not perform an activity, a problem-solving module appears in which the user must select from various strategies that may aid him/her in performing the task (strategies were provided by therapist stakeholders).

Group 3, Gaming CI therapy with additional contact via video conference. This group will receive treatment that is identical to Group 2, but will receive an additional 6 brief video conference consultations throughout the treatment period so that this group receives the same number of therapist encounters as the CI therapy group.

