- 6. Repeat the 9 shaping tasks from TD2; can now consider shaping the tasks—document on **Task List**, **Shaping Data Sheets** and **Shaping Graphs**
- 7. Select the 10 items for the Home Skill Assignment (HSA) list
- 8. Give the patient the next Home Achievement Record form
- 9. Ask participant about adverse events and fill out **Adverse Event Reporting Form** if need be
- 10. Ask participant if he/she watched the CIMT videos on YouTube. If they have not yet, assign as homework.
- 11. Turn video camera off and add comments to **Therapist Treatment Recording Log**
- 12. Store the video on the encrypted hard drive under the correct group and session subfolder

How to reset mitt device

- 1. Unscrew 4 outer edge corners (Red Arrows)
- 2. Hold down black button for ~5 seconds (Blue Arrow)
- 3. Re-screw 4 outer edge corners

MAL in follow-up
MAL How Well administered with problem solving weekly for 1st month via phone. 20 min. each. (4 times total)

• Record responses on MAL spreadsheet

Description of Therapy

Constraint Induced Movement Therapy or CI therapy is thought to work because it has been shown to produce a large "rewiring" of the brain; that is, after treatment, a larger part of the brain is involved in producing movement of the weaker arm than before therapy. It also has the effect of overcoming a strong tendency not to use the weaker arm ("learned nonuse") that develops in the early post-stroke period.

Research has shown that patients can "learn" to improve the motor ability of the weaker parts of their bodies and thus cease to rely exclusively or primarily on the stronger parts. For this learning and rewiring to occur, two things have to happen:

- 1. Intensive training of the weaker arm in the clinic. This will occur through intensive training of the weaker arm and hand in the laboratory for 3 hours a day for 10 days.
- 2. Use of the weaker arm for daily activities (more than the stronger arm) OUTSIDE the clinic. This is linked to structural changes in the brain and improved quality of life. Research has shown that these improvements are absent when improved motor function does not carry over to daily life. Three things will help you carry-over in-lab improvements to your daily activities.
 - a. Restraint of the stronger arm in a **padded mitt** for a large number of waking hours over the treatment period in the laboratory and at home.

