- 1. TOTAL PLAY TIME SHOULD BE 15 HOURS OVER 3 WEEKS.
- 2. Occurs in home on participants' own schedule. 1.5 hours per day on 10 treatment days. Participants are encouraged to break this down into at least 3 separate play sessions per day (15-30 min sessions are optimal).
- 3. Missed game play should be made up during off days.

In-clinic Treatment Days ~Days 2, 3, 4 (1 hour)

- 1. Turn video camera on & say participant ID, treatment day, and group
- 2. Check game play compliance
 - a. Click on Report Generator App (cannot be opened behind firewall)
 - b. A black box pops up that says "Input User ID"
 - c. Enter the participant's Game ID under the "Input User ID" prompt (this ID is found on the participant's business card)
 - d. Hit Enter
 - e. Report is generated (it works best if the computer you're working from has Excel)
- 3. Check compliance with smart watch. Review daily movement counts/problem-solve if low use.
- 4. Review in-game MAL with problem-solving.
- 5. Review **Home Achievement Record** with problem-solving.
- 6. **Home Skill Assignment**, 10 items (may be same or different than 1st HSA).
- 7. Remind participant about computerized MAL for next 4 weeks.
- 8. Ask participant about adverse events and fill out **Adverse Event Reporting Form** if need be
- 9. Ask participant if he/she watched the CIMT videos on YouTube. If he/she has not, assign as homework.
- 10. Turn video camera off and add comments to Therapist Treatment Recording Log
- 11. Store the video on the encrypted hard drive under the correct group and session subfolder

Follow-up

MAL administered through REDCap survey or mail if no internet access weekly for 4
weeks.

Checklist Tele-Gaming

Note: Bolded items are separate sheets within the treatment packet to be completed

Prior to Treatment (after pre-test)

- 1. Provide the activity monitors to participants and demonstrate use.
- 2. Instruct them to wear the activity monitors on both arms for 2 days before treatment to establish a baseline of arm use.
- 3. Make sure participant knows to charge them overnight every night.
- 4. Provide the smart watch to participants and demonstrate use (give them the **instructions** to take home with them).
- 5. Instruct them to wear the watch on the less affected arm for 2 days before treatment to establish a baseline of "normal" arm movement counts.
- 6. Have them record the values on the watch right before going to bed on the **Limb Activation Log**.

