- 6. **Home Skill Assignment**, 10 items (may be same or different than 1st HSA).
- 7. Ask participant about adverse events and fill out **Adverse Event Reporting Form** if need be.
- 8. Ask participant if he/she watched the CIMT videos on YouTube. If he/she has not, assign as homework.
- 9. Turn video camera off and add comments to Therapist Treatment Recording Log
- 10. Store the video on the encrypted hard drive under the correct group and session subfolder

Video consultation Days 4, 6, 7, 9, 10 (20 min)

- 1. Turn video camera on & say participant ID, treatment day, and group
- 2. Review in-game MAL with problem-solving. (10 min)
 - a. Click on Report Generator App (cannot be opened behind firewall)
 - b. A black box pops up that says "Input User ID"
 - c. Enter the participant's Game ID under the "Input User ID" prompt (this ID is found on the participant's business card)
 - d. Hit Enter
 - e. Report is generated (it works best if the computer you're working from has Excel)
- 3. Review **Home Achievement Record** with problem-solving (5 min)
- 4. **Home Skill Assignment**, 10 items (may be same or different than 1st HSA). (5 min)
- 5. Remind participant about computerized MAL for next 4 weeks.
- 6. Ask participant if he/she watched the CIMT videos on YouTube. If he/she has not, assign as homework.
- 7. Ask participant about adverse events and fill out **Adverse Event Reporting Form** if need be
- 8. Turn video camera off and add comments to Therapist Treatment Recording Log
- 9. Store the video on the encrypted hard drive under the correct group and session subfolder

Follow-up

1. MAL administered via phone call weekly for 4 weeks. Therapist is to complete the **MAL in follow-up document** each time.

Description of Therapy

What is CI Therapy?

Constraint Induced Movement Therapy or CI therapy is thought to work because it has been shown to produce a large "rewiring" of the brain; that is, after treatment, a larger part of the brain is involved in producing movement of the weaker arm than before therapy. It also has the effect of overcoming a strong tendency not to use the weaker arm ("learned nonuse") that develops in the early post-stroke period.

Research has shown that patients can "learn" to improve the motor ability of the weaker parts of their bodies and thus cease to rely exclusively or primarily on the stronger parts. For this learning and rewiring to occur, two things have to happen:

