9 (tele)	
10 (tele)	

MAL in Follow-up Recording Form for Tele-Gaming Group:

MAL Spreadsheet (How Well Scale Only)	F/U 1	F/U 2	F/U 3	F/U 4
1. Turn on a light switch				
2. Open drawer				
3. Remove an item of clothing from a drawer				
4. Pick up phone				
5. Wipe off a kitchen counter or other surface				
6. Get out of car				
7. Open refrigerator				
8. Open a door by turning a door knob/handle				
9. Use a TV remote control				
10. Wash your hands (lathering and rinsing hands)				
11. Turning water on/off with knob/lever on faucet				
12. Dry your hands				
13. Put on your socks				
14. Take off your socks				
15. Put on your shoes				
16. Take off your shoes				
17. Get up from a chair with armrests				
18. Pull chair away from table before sitting down				
19. Pull chair toward table after sitting down				
20. Pick up a glass, bottle, drinking cup, or can				
21. Brush your teeth				
22. Use a key to unlock a door				
23. Carry an object in your hand				
24. Use a fork or spoon for eating				
25. Comb your hair				
26. Pick up a cup by a handle				
27. Button a shirt				
28. Eat half a sandwich or finger foods				
MEAN				

Limb Activation Instructions (Pebble Watch):

- If the screen is showing the time, press "select"
- Toggle down to the app "Hands On"
- Push the select button to select the Hands On app (this is the limb activation)
- When you are using the device, make sure notifications are on (see above picture for how to turn them on/off)
- IMPORTANT: In order for the notifications to work (vibrate after 10 minutes of inactivity), you must click the "back" button and you will wear it with the time visible, not the amount of movements
- However, if you prefer to have the daily count visible, that is fine too, the notifications just will not work
- Wear the watch during all of your waking hours for the duration of your participation in the study
- The watch will need to be charged every night
 - o The charger will insert into a USB on any computer and connect to the back of the watch
 - o The display on the watch will say "charging" when it's connected properly
- To reset the app, hold down the select button for a few seconds and release and everything will be set back to 0

Pebble Watch Log:

- > Please record the daily count from your watch each night before you go to bed

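### By 6 months Group 3 differs from Group 2 by four weekly therapist phone contacts as well as six video consultations, so a 6-month difference cannot be put down to video contact alone

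*Combined protocol and SAP*

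**What the plan says.** In Detailed Study Procedures, the Group 3 paragraph states: "This group will receive treatment that is identical to Group 2, but will receive an additional 6 brief video conference consultations". It places these consultations in the treatment period and says they bring Group 3 to the same number of therapist encounters as the CI therapy arm. Research Design gives the purpose of the contrast: "The comparison between groups 2 and group 3 will determine the extent to which additional therapist monitoring via video conference improves treatment response". It sets no time limit on that claim, and the same paragraph lists outcomes before treatment, after treatment and 6 months later.

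The treatment packets describe what happens in the weeks after treatment:

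- Group 2 (Checklist Self-Gaming, Follow-up): "MAL administered through REDCap survey or mail if no internet access weekly for 4" weeks.
- Group 3 (Checklist Tele-Gaming, Follow-up): "MAL administered via phone call weekly for 4 weeks", with the therapist to complete a follow-up document each time. The packet includes that document, headed "MAL in Follow-up Recording Form for Tele-Gaming Group", with four follow-up columns.
- Group 1 (CI therapy checklist, MAL in follow-up): "MAL How Well administered with problem solving weekly for 1st month via phone", four calls of 20 minutes.
- Group 4 (Traditional Therapy Checklist): no follow-up contact is listed.

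Neither the arm descriptions nor the Timeline of Participation table mentions these contacts.

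**The concern.** The Group 2 v Group 3 contrast is meant to answer one question: does added therapist contact by video improve the response to home gaming? At 6 months the arms differ in two ways, video sessions during treatment and live therapist phone contact after it. No planned analysis separates the two.

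Two features of the plan make this more than a clerical matter. First, the 6-month visit is an outcome time, and Data Analysis makes the treatment-by-time interaction the effect of primary interest. Second, the MAL has two roles. Aim 4a and the Measurement section list it as a primary measure, and the protocol also treats its administration as part of the transfer package. Repeated therapist-led administration in one arm might therefore act as treatment, or might change how participants later rate themselves on the same instrument. A reader following Research Design as written would credit either effect to video conferencing.

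**Working it through.** **Inputs**

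- Group 3 video sessions: one of 60 min (day 2) and five of 20 min (days 4, 6, 7, 9, 10), from Checklist Tele-Gaming.
- Clinic visits: four in each gaming arm, from the Self-Gaming and Tele-Gaming checklists and recording logs.
- Group 3 teleconsultation time: 2.6 h, from the Timeline of Participation table, in the column for therapy weeks 2 to 4.
- Follow-up phone contacts: four in Group 3 and none in Group 2, from the Follow-up sections.
- Length of a Group 3 follow-up call: not stated. Assumed range 5 to 30 min. The 20-min case borrows the length given for Group 1's calls.

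**Step 1: reproduce the stated contact.** Video time = 60 + 5 × 20 = 160 min = 2.67 h, against 2.6 h stated. The gap is (2.67 − 2.6)/2.6 = 2.6%, consistent with truncation. Encounters during treatment are 4 clinic + 6 video = 10 in Group 3, equal to the 10 CI therapy days, and 4 in Group 2. The stated figures hold for the treatment period and are fully accounted for by the video sessions; they contain no phone time.

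**Step 2: count live contacts up to the 6-month visit.** Extra contacts in Group 3 over Group 2 = 6 video + 4 phone = 10, against 6 in the protocol text. The calls are 4/10 = 40% of the extra contacts. This count needs no assumption about call length.

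**Step 3: share of extra contact time.** Share = 4m / (160 + 4m), where m is minutes per call.

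| Assumed min per call | Phone min | Total extra min | Phone share |
|---|---|---|---|
| 5 | 20 | 180 | 11% |
| 10 | 40 | 200 | 20% |
| 20 | 80 | 240 | 33% |
| 30 | 120 | 280 | 43% |

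**Step 4: place the calls in time.** Post-treatment testing falls in the week after treatment and follow-up at 6 months, give or take one month. Four weekly calls after treatment end well before the 6-month window opens. The first could fall in the same week as post-treatment testing, and the documents do not give the order. The pre-to-post contrast is therefore largely, though not demonstrably wholly, free of phone contact.

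**Step 5: check that the packet agrees with itself.** For the short video sessions, Checklist Tele-Gaming tells the therapist to remind the participant of a computerized MAL over the next four weeks. The same reminder stands in Checklist Self-Gaming. Whether Group 3's phone MAL replaces or adds to a computerized one is not stated.

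**The case against.** The strongest reply is that the Group 3 sentence and the tabulated hours concern treatment in weeks 2 to 4, so follow-up calls do not contradict them. That stands: a reader might infer that the contact hours are wrong, but they reproduce for the period they cover. It does not rescue the Research Design claim, which has no such limit while outcomes run to 6 months.

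A second reply is that the calls may have little therapeutic content. A reader might infer that Group 3 alone receives follow-up MAL, or that its calls are further problem-solving therapy. The documents support neither. Group 2 also completes a weekly MAL for four weeks, so self-monitoring is shared. Problem solving is written only for Group 1's calls; the Group 3 form holds item scores and a mean. The protocol's remark on the special importance of the MAL concerns daily, not weekly, administration. The documented difference is therefore live therapist administration against self-completion, with an effect of unknown size.

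A third reply is that Detailed Study Procedures also describes a wider aim, the effect of differing amounts of therapist contact across gaming conditions, and that Data Analysis names an overall four-group interaction and no separate 6-month test of Group 2 v Group 3. Under the wider aim, phone contact belongs to the contrast. That supports the relabelling proposed here; it does not support attribution to video.

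Finally, a reader might extend the problem equally to every 6-month contrast. That goes too far. Groups 1 and 3 are matched on the number of follow-up calls. Groups 1 and 2 already differ by 35 v 5 contact hours and by the mitt; Group 1's calls total 4 × 20 = 80 min, or 80/2,100 = 3.8% of its 35 hours. Group 4 lacks the whole transfer package, so Group 2 v Group 4 never isolated one ingredient.

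**Conclusion.** The point holds for the 6-month comparison of Groups 2 and 3. By that visit the planned difference is ten live therapist contacts, six by video and four by phone, not six. In time, the phone share of the extra contact is 11% to 43% over an assumed 5 to 30 min per call; no single figure in that range can be defended, because the documents give no call length. The count of ten rests on the checklists being followed as written.

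Whether the calls change outcomes is unknown, and nothing here shows that they do. What follows is limited to attribution: a 6-month difference between these arms could not be ascribed to video contact alone. Randomization, the mixed model and the stated treatment-period hours are not called into question. The pre-to-post contrast is largely unaffected, subject to the unstated timing of the first call.

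**What to change.** Reconcile Research Design, the Group 3 paragraph, the Follow-up sections of the Self-Gaming and Tele-Gaming checklists, and the Tele-Gaming follow-up form on MAL contact after treatment. Say whether Group 3's phone MAL replaces or adds to the computerized MAL mentioned in its own checklist. State the post-treatment contact for every arm, including Group 1's four 20-minute calls and whether Group 4 has any. Which follow-up procedure each arm should have is for the investigators to settle.

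If the difference between Groups 2 and 3 stays, make two changes to the analysis and reporting text:

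- Rest any statement about video contact on the pre-to-post change, and state whether any follow-up call precedes post-treatment testing.
- Describe the 6-month Group 2 v Group 3 result as the effect of video plus follow-up phone contact.

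This is a change of wording and needs no new data. Its cost is a narrower 6-month claim.
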